3.2.4 Pharmacokinetics

Absorption: Following administration of a single 25 mg dose of temsirolimus in patients with cancer, mean temsirolimus C_{max} in whole blood was 585 ng/mL (coefficient of variation, CV =14%), and mean AUC in blood was 1627 ng•h/mL (CV=26%). Typically C_{max} occurred at the end of infusion. Over the dose range of 1 mg to 25 mg, temsirolimus exposure increased in a less than dose proportional manner while

sirolimus exposure increased proportionally with dose. Following a single 25 mg intravenous dose in patients with cancer, sirolimus AUC was 2.7-fold that of temsirolimus AUC, due principally to the longer half-life of sirolimus.

Distribution: Following a single 25 mg intravenous dose, mean steady-state volume of distribution of temsirolimus in whole blood of patients with cancer was 172 liters. Both temsirolimus and sirolimus are extensively partitioned into formed blood elements.

Metabolism: Cytochrome P450 3A4 is the major isozyme responsible for the formation of five temsirolimus metabolites. Sirolimus, an active metabolite of temsirolimus, is the principal metabolite in humans following intravenous treatment. The remainder of the metabolites account for less than 10% of radioactivity in the plasma. In human liver microsomes temsirolimus was an inhibitor of CYP2D6 and 3A4. However, there was no effect observed in vivo when temsirolimus was administered with desipramine (a CYP2D6 substrate), and no effect is anticipated with substrates of CYP3A4 metabolism.

Elimination: Elimination is primarily via the feces. After a single IV dose of [¹⁴C]-temsirolimus approximately 82% of total radioactivity was eliminated within 14 days, with 4.6% and 78% of the administered radioactivity recovered in the urine and feces, respectively. Following a single 25 mg dose of temsirolimus in patients with cancer, temsirolimus mean (CV) systemic clearance was 16.2 (22%) L/h. Temsirolimus exhibits a bi-exponential decline in whole blood concentrations and the mean half-lives of temsirolimus and sirolimus were 17.3 hr and 54.6 hr, respectively.

Drug Interactions: Co-administration of temsirolimus with rifampin, a potent CYP3A4/5 inducer, had no significant effect on temsirolimus C_{max} (maximum concentration) and AUC (area under the concentration versus the time curve) after intravenous administration, but decreased sirolimus C_{max} by 65% and AUC by 56% compared to temsirolimus treatment alone. If alternative treatment cannot be administered, a dose adjustment should be considered. Co-administration of temsirolimus with ketoconazole, a potent CYP3A4 inhibitor, had no significant effect on temsirolimus C_{max} or AUC; however, sirolimus AUC increased 3.1-fold, and C_{max} increased 2.2-fold compared to temsirolimus alone. If alternative treatment cannot be administered, a dose adjustment should be considered. The concentration of desipramine, a CYP2D6 substrate, was unaffected when 25 mg of temsirolimus was co-administered. No clinically significant effect is anticipated when temsirolimus is co-administered with agents that are metabolized by CYP2D6 or CYP3A4.

3.2.4.1 Temsirolimus Drug Interactions

Concomitant Strong CYP3A4 Inhibitors: The concomitant use of strong CYP3A4 inhibitors should be avoided (e.g. ketoconazole, itraconazole, clarithromycin,

atazanavir, indinavir, nefazodone, nelfinavir, ritonavir, saquinavir, telithromycin, and voriconazole). Grapefruit juice may also increase plasma concentrations of sirolimus (a major metabolite of temsirolimus) and should be avoided. If patients must be co-administered a strong CYP3A4 inhibitor, based on pharmacokinetic studies, a temsirolimus dose reduction to 12.5 mg/week should be considered. This dose of temsirolimus is predicted to adjust the AUC to the range observed without inhibitors.

However, there are no clinical data with this dose adjustment in patients receiving strong CYP3A4 inhibitors. If the strong inhibitor is discontinued, a washout period of approximately 1 week should be allowed before the temsirolimus dose is adjusted back to the dose used prior to initiation of the strong CYP3A4 inhibitor. (see previous table in 6.1.1.3)

Concomitant Strong CYP3A4 Inducers: The use of concomitant strong CYP3A4 inducers should be avoided (e.g. dexamethasone, phenytoin, carbamazepine, rifampin, rifabutin, rifampacin, phenobarbital). If patients must be co-administered a strong CYP3A4 inducer, based on pharmacokinetic studies, a temsirolimus dose increase from 25 mg/week up to 50 mg/week should be considered. This dose of temsirolimus is predicted to adjust the AUC to the range observed without inducers. However, there are no clinical data with this dose adjustment in patients receiving strong CYP3A4 inducers. If the strong inducer is discontinued the temsirolimus dose should be returned to the dose used prior to initiation of the strong CYP3A4 inducer

3.2.5 Clinical Safety

Hypersensitivity Reactions

Hypersensitivity reactions manifested by symptoms including, but not limited to, anaphylaxis, dyspnea, flushing, and chest pain have been observed with temsirolimus. Temsirolimus should be used with caution in persons with known hypersensitivity to temsirolimus or its metabolites (including sirolimus), polysorbate 80, or to any other component (including the excipients) of temsirolimus.

An H1 antihistamine should be administered to patients before the start of the intravenous temsirolimus infusion. Temsirolimus should be used with caution in patients with known hypersensitivity to an antihistamine, or patients who cannot receive an antihistamine for other medical reasons.

If a patient develops a hypersensitivity reaction during the temsirolimus infusion, the infusion should be stopped and the patient should be observed for at least 30 to 60 minutes (depending on the severity of the reaction). At the discretion of the physician, treatment may be resumed with the administration of an H1-receptor antagonist (such

as diphenhydramine), if not previously administered, and/or an H2-receptor antagonist (such as intravenous famotidine 20 mg or intravenous ranitidine 50 mg) approximately 30 minutes before restarting the temsirolimus infusion. The infusion may then be resumed at a slower rate (up to 60 minutes).

Hepatic Impairment

The safety and pharmacokinetics of temsirolimus were evaluated in a dose escalation phase 1 study in 110 patients with normal or varying degrees of hepatic impairment. Patients with baseline bilirubin $>1.5 \times \text{ULN}$ experienced greater toxicity than patients with baseline bilirubin $\leq 1.5 \times \text{ULN}$ when treated with temsirolimus. The overall frequency of \geq grade 3 adverse reactions and deaths, including deaths due to progressive disease, were greater in patients with baseline bilirubin $>1.5 \times \text{ULN}$. temsirolimus is contraindicated in patients with bilirubin $>1.5 \times \text{ULN}$ due to increased risk of death. Use caution when treating patients with mild hepatic impairment. Concentrations of temsirolimus and its metabolite sirolimus were increased in patients with elevated AST or bilirubin levels. If temsirolimus must be given in patients with mild hepatic impairment (bilirubin $>1 - 1.5 \times \text{ULN}$ or AST $>\text{ULN}$ but bilirubin $\leq \text{ULN}$), reduce the dose of temsirolimus to 15 mg/week.

Hyperglycemia/Glucose Intolerance

The use of temsirolimus is likely to result in increases in serum glucose. In the phase 3 trial, 89% of patients receiving temsirolimus had at least one elevated serum glucose while on treatment, and 26% of patients reported hyperglycemia as an adverse event. This may result in the need for an increase in the dose of, or initiation of, insulin and/or oral hypoglycemic agent therapy. Serum glucose should be tested before and during treatment with temsirolimus. Patients should be advised to report excessive thirst or any increase in the volume or frequency of urination.

Infections

The use of temsirolimus may result in immunosuppression. Patients should be carefully observed for the occurrence of infections, including opportunistic infections

Interstitial Lung Disease

Cases of interstitial lung disease, some resulting in death, occurred in patients who received temsirolimus. Some patients were asymptomatic with infiltrates detected on computed tomography scan or chest radiograph. Others presented with symptoms such as dyspnea, cough, hypoxia, and fever. Some patients required discontinuation of temsirolimus and/or treatment with corticosteroids and/or antibiotics, while some patients continued treatment without additional intervention. Patients should be advised to report promptly any new or worsening respiratory symptoms.

Hyperlipemia

The use of temsirolimus is likely to result in increases in serum triglycerides and cholesterol. In the phase 3 trial, 87% of patients receiving temsirolimus had at least one elevated serum cholesterol value and 83% had at least one elevated serum triglyceride value. This may require initiation, or increase in the dose, of lipid-lowering agents. Serum cholesterol and triglycerides should be tested before and during treatment with temsirolimus.

Bowel Perforation

Cases of fatal bowel perforation occurred in patients who received temsirolimus. These patients presented with fever, abdominal pain, metabolic acidosis, bloody stools, diarrhea, and/or acute abdomen. Patients should be advised to report promptly any new or worsening abdominal pain or blood in their stools.

Renal Failure

Cases of rapidly progressive and sometimes fatal acute renal failure not clearly related to disease progression occurred in patients who received temsirolimus. Some of these cases were not responsive to dialysis.

Wound Healing Complications

Use of temsirolimus has been associated with abnormal wound healing. Therefore, caution should be exercised with the use of temsirolimus in the perioperative period.

Intracerebral Hemorrhage

Patients with central nervous system tumors (primary CNS tumor or metastases) and/or receiving anticoagulation therapy may be at an increased risk of developing intracerebral bleeding (including fatal outcomes) while receiving temsirolimus.

Co-administration with Inducers or Inhibitors of CYP3A Metabolism

Agents Inducing CYP3A Metabolism:

Strong inducers of CYP3A4/5 such as dexamethasone, carbamazepine, phenytoin, phenobarbital, rifampin, rifabutin, and rifampacin may decrease exposure of the active metabolite, sirolimus. If alternative treatment cannot be administered, a dose adjustment should be considered. St. John's Wort may decrease temsirolimus plasma concentrations unpredictably. Patients receiving temsirolimus should not take St. John's Wort concomitantly.

Agents Inhibiting CYP3A Metabolism:

Strong CYP3A4 inhibitors such as atazanavir, clarithromycin, indinavir, itraconazole, ketoconazole, nefazodone, nelfinavir, ritonavir, saquinavir, and telithromycin may

increase blood concentrations of the active metabolite sirolimus. If alternative treatments cannot be administered, a dose adjustment should be considered.

Vaccinations

The use of live vaccines and close contact with those who have received live vaccines should be avoided during treatment with temsirolimus. Examples of live vaccines are: intranasal influenza, measles, mumps, rubella, oral polio, BCG, yellow fever, varicella, and TY21a typhoid vaccines.

Pregnancy

Pregnancy Category D: Temsirolimus administered daily as an oral formulation caused embryo-fetal and intrauterine toxicities in rats and rabbits at human sub-therapeutic exposures. Embryo-fetal adverse effects in rats consisted of reduced fetal weight and reduced ossifications, and in rabbits included reduced fetal weight, omphalocele, bifurcated sternabrae, notched ribs, and incomplete ossifications. In rats, the intrauterine and embryo-fetal adverse effects were observed at the oral dose of 2.7 mg/m²/day (approximately 0.04-fold the AUC in cancer patients at the human recommended dose). In rabbits, the intrauterine and embryo-fetal adverse effects were observed at the oral dose of ≥ 7.2 mg/m²/day (approximately 0.12-fold the AUC in cancer patients at the recommended human dose).

Women of childbearing potential should be advised to avoid becoming pregnant throughout treatment and for 3 months after temsirolimus therapy has stopped. Temsirolimus can cause fetal harm when administered to a pregnant woman. If this drug is used during pregnancy, or if the patient becomes pregnant while taking this drug, the patient should be apprised of the potential hazard to the fetus.

Men should be counseled regarding the effects of temsirolimus on the fetus and sperm prior to starting treatment. Men with partners of childbearing potential should use reliable contraception throughout treatment and are recommended to continue this for 3 months after the last dose of temsirolimus.

4.0 ELIGIBILITY CRITERIA

4.1 INCLUSION

1. Pathologic confirmation of metastatic or locally advanced RCC with a major clear cell component.
2. Measurable disease by RECIST criteria.
3. Age ≥ 18 years

4. ECOG performance status 0-2 or Karnofsky Performance Status \geq 60%
5. Meets criteria for poor-risk defined as 3 or more of the following: ECOG performance status 2, anemia (hemoglobin lower than reference range), elevated serum LDH $>1.5x$ upper limit of normal (ULN), hypercalcemia (corrected serum calcium level $>$ upper limit of normal), time from initial RCC diagnosis to registration on this trial $<$ 1 year, and $>$ 1 metastatic organ sites.
6. Adequate organ and marrow function within 14 days of registration as defined below:
 - Absolute neutrophil count $\geq 1,500/\mu\text{L}$
 - Platelets $\geq 100,000/\mu\text{L}$
 - Hgb ≥ 9.0 g/dL (transfusion allowed)
 - Renal: serum creatinine $\leq 1.5 \times$ ULN or calculated CrCl ≥ 40 cc/min and random urine protein:creatinine ratio (UPC) $<$ 1 or 24-hr urine protein $<$ 1g
 - Liver: total bilirubin ≤ 1.5 mg/dl; AST (SGOT) and ALT (SGPT) $\leq 2.5 \times$ ULN for subjects without evidence of liver metastases, $\leq 5 \times$ ULN for subjects with documented liver metastases
 - INR $\leq 1.2 \times$ ULN; PTT $\leq 1.5 \times$ ULN. Therapeutic anticoagulation with warfarin is allowed if target INR ≤ 3 on a stable dose of warfarin or on a stable dose of LMW heparin for $>$ 2 weeks (14 days) at time of randomization.
7. Female patients of childbearing potential (not postmenopausal for at least 12 months and not surgically sterile) must have a negative serum or urine pregnancy test within 14 days of study registration. Pregnancy test must be repeated if performed $>$ 14 days before starting study drug.

4.2 EXCLUSION

1. Prior malignancy, except for non-melanoma skin cancer, in situ carcinoma of any site, or other cancers for which the patient has been adequately treated and disease free for 2 years
2. Prior targeted therapy (anti-VEGF agents or mTOR inhibitors) including adjuvant therapy, and prior chemotherapy for mRCC. However, prior immunotherapy (cytokines or vaccines) is allowed.
3. Any experimental drug while on this study; however, concomitant bone targeted therapy (bisphosphonates or the anti-RANK ligand denosumab) is allowed.

4. Uncontrolled brain metastases and infections. Patients with brain metastases treated with Gamma Knife (GK) or with whole brain radiation within 24 hours of registration.
5. History of stroke within 6 months of registration
6. Clinically significant cardiovascular disease, defined as myocardial infarction (or unstable angina) within 6 months of registration, New York Heart Association (NYHA) Grade II or greater congestive heart failure, serious cardiac dysrhythmia refractory to medical management. However, treated and controlled or stable/not clinically significant cardiovascular disease is allowed per evaluation by cardiologist.
7. Uncontrolled hypertension (home blood pressure readings are permitted) or prior history of hypertensive crisis or hypertensive encephalopathy; however, treatment of hypertension with medications is permitted.
8. History of uncontrolled hemoptysis ($\geq 1/2$ teaspoon of bright red blood per episode) within 1 month prior to Day 1
9. Significant vascular disease including aortic aneurysm, aortic dissection.
10. Symptomatic peripheral vascular disease
11. Pregnancy
12. HIV-positive patients receiving combination anti-retroviral therapy
13. Coagulopathy or bleeding diathesis
14. Concomitant treatment with rifampin, St. John's wort, or the cytochrome p450 enzyme-inducing antiepileptic drugs (phenytoin, carbamazepine or Phenobarbital)
15. Major surgery within 28 days prior to registration
16. Core biopsy or other minor surgical procedure, excluding placement of a vascular access device within 7 days prior to starting drug
17. History of abdominal fistula, gastrointestinal perforation, or intra-abdominal abscess within 6 months prior to study registration
18. Serious non-healing wound
19. Baseline QT_cB ≥ 470 msec.

[figure not shown]
5.0 TREATMENT PLAN

5.1 Study Summary

Patients with advanced poor-risk clear-cell RCC who have not had any prior systemic targeted therapy will be randomized fairly in a 1:1 ratio to receive pazopanib or temsirolimus as first-line therapy. Patients will be stratified upfront by nephrectomy status (yes/no) and prior cytokine/vaccine therapy (yes/no). At the time of disease progression, patients will be offered the option of crossover to receive the agent they did not receive in the first-line.

5.2 Administration

After registration on the protocol, patients will be randomized to receive either pazopanib or temsirolimus treatment. Following randomization patients will begin treatment with the first assigned agent. At progression, if they have not suffered an adverse event that would preclude them from continuing with systemic therapy, after the applicable washout period, will begin treatment with the remaining treatment agent at the discretion of the physician.

Pazopanib will be taken at 800 mg PO daily without food (at least 1 hour before or 2 hours after a meal) until PD or prohibitive toxicity or withdrawal of consent. Tablets will not be crushed due to the potential for increased rate of absorption which may affect systemic exposure. If a dose is missed, it should not be taken if it is less than 12 hours until the next dose. Patients will complete a pill diary for pazopanib to document compliance.

Temsirolimus will be given at 25 mg IV infused over 30-60 minutes every week until PD or prohibitive toxicity or withdrawal of consent. Patients will receive prophylactic intravenous diphenhydramine 25 to 50 mg (or similar antihistamine) approximately 30 minutes before the start of each dose of temsirolimus.

A cycle consists of 4 weeks of therapy. Pazopanib will be self-administered at home and in the outpatient setting for patients who receive temsirolimus.

All patients will have a washout period of 2 weeks from the day of progressive disease tumor assessment before they start 2nd-line therapy.

5.3 Evaluation before treatment

Within 4 weeks of registration:

* A standing window of allowance equal to +/- 3 days will be utilized.

- All participants must sign a consent form agreeing to participate in the study
- Baseline radiological studies should include CT scans of the chest (high-resolution) and abdomen and MRI of the brain. Additional studies (e.g., CT scan of pelvis, bone scan, plain films) should be obtained as appropriate. MRI of the abdomen and/or CT scan of the brain can be substituted at the physician's discretion.
- Cardiac evaluation with a 12-lead EKG and an echocardiogram or MUGA. The echocardiogram or MUGA scan may be obtained within 12 weeks of registration.
- A minimum of 7 days must elapse between the diagnostic biopsy and treatment if tissue diagnosis was not previously made.
- Optional: Previously collected tissue will be requested from patients who consent, and will be stored for future research related to cancer. Tissue will also be collected during procedures performed while patients are enrolled in this study. No new procedures will be required. This tissue will also be banked as described above.

5.3.1 Within 14 days of registration:

* A standing window of allowance equal to +/- 2 days will be utilized.

- All patients must undergo a complete history and physical examination, including vital signs, ECOG performance status, height, current weight including recent weight loss, Concurrent non-malignant disease and medications must be documented. All prior surgical procedures or radiation treatments must be recorded in detail.
- Laboratory studies should include CBC w/ platelet count and differential, chemistry panel (total protein, albumin, alkaline phosphatase, AST, ALT, calcium, LDH, total bilirubin, BUN, creatinine, phosphorus, glucose, sodium, potassium, chloride, carbon dioxide), fasting lipid panel, free T4, thyroid stimulating hormone (TSH), PT and PTT. Serum amylase and lipase will be done only if clinically indicated. Patients will have a U/A. Patients who have urine protein ≥ 300 on U/A should have a random UPC ratio at baseline. A pregnancy test (serum/plasma or urine betaHCG) in female patients of childbearing potential will also be included.

- All patients will complete a full Quality of Life assessment battery (see Section 7 for additional details)
- Optional baseline blood specimens for future correlative studies will be collected.

5.4 Evaluation During Treatment (initial treatment or crossover)

*Evaluations while on study will have a standing window of allowance equal to +/- 7 days.

Treatment evaluations will consist of the following study activities (a cycle is 4 weeks):

- Interim medical history and physical examination, including vital signs, height, current weight including recent weight loss every 4 weeks for temsirolimus patients. (May be done by local physician every other cycle for temsirolimus patients only). Interim medical history and physical examination, including vital signs, current weight including recent weight loss every 8 weeks for pazopanib patients.
- All patients will complete a follow-up Quality of Life assessment battery (see Section 7 for additional details)
- Weekly blood pressure monitoring for the first four weeks for patients receiving pazopanib, and then with each history and physical every 8 weeks. Monitoring may be performed at doctor's office or by the patient at home using an electronic blood pressure device. Blood pressure measurements performed outside of the office of the treating physician should be recorded by the patient and submitted to the treating physician during cycle one. An increase in blood pressure to > 160 systolic or > 100 diastolic should be reported to the treating physician immediately.
- Urinalysis (U/A) every 8 weeks. Patients who have urine protein ≥ 300 on U/A should have a random UPC ratio checked for pazopanib patients only.
- Patients on Pazopanib will have serum chemistry and electrolytes including total protein, albumin, alkaline phosphatase, AST, ALT, calcium, LDH, total bilirubin, BUN, creatinine, phosphorus, glucose, sodium, potassium, chloride, and carbon dioxide will be done every 2 weeks for the first 8 weeks and 8 weeks x 2, and every 16 weeks thereafter. Pazopanib patients will have CBC with platelet count and differential every 2 weeks for the first 8 weeks, every 8 weeks x 2, and every 16 weeks thereafter.
- Patients on temsirolimus will have serum chemistry and electrolytes including total protein, albumin, alkaline phosphatase, AST, ALT, calcium, LDH, total bilirubin, BUN, creatinine, phosphorus, glucose, sodium, potassium, chloride, and carbon dioxide will be done every 2 weeks for the first 8 weeks and every 4 weeks thereafter. Fasting lipid panel every 4 weeks for the first 8 weeks, every 8 weeks x 2, and every 16 weeks thereafter. CBC with platelet count and differential will be done every week for patients on temsirolimus.

- Record concomitant medications with each history and physical.
- Reconcile the medication diary provided during treatment with each history and physical for those on pazopanib.
- Adverse events will be assessed at each visit and monitored throughout the study.
- 12-Lead Electrocardiogram will be repeated at Cycle 2 Day 1, 12 weeks later, and every 16 weeks after that for patients on Pazopanib. (see Section 6.1.1.4 for additional details of QT interval monitoring) Patients receiving temsirolimus will have an ECG done every 16 weeks.
- Optional blood specimens for future correlative studies will be obtained every 8 weeks and at progression.
- Serum amylase and lipase will be obtained only as clinically indicated.
- Serum T4 and TSH will be obtained every 8 weeks for patients receiving pazopanib.
- Repeat radiological studies (CT, MRI as indicated) to evaluate response every 8 weeks. Studies to confirm a complete response or document progressive disease will be performed as needed. Patients who are progression free after 1 year can have their imaging studies obtained every 16 weeks.
- Echocardiogram or MUGA scan (echocardiogram preferred) will be repeated every 24 weeks and as clinically indicated.

Outside Physician Participation During Treatment (Temsirrolimus Patients may have interim infusions with local MD)

1. MDACC Physician communication with the outside physician is required prior to the patient returning to the local physician. This will be documented in the patient record
2. A letter to the local physician outlining the patient's participation in a clinical trial will request local physician agreement to supervise the patient's care (Appendix J); A copy of the protocol abstract and evaluation during treatment will be provided to the local physician with the letter.
3. Protocol required evaluations outside MDACC will be documented by telephone, fax or e-mail. Fax and/or e-mail will be dated and signed by the MDACC physician, indicating that they have reviewed it.
4. Changes in drug dose and/or schedule must be discussed with and approved by the MDACC physician investigator, or their representative prior to initiation, and will be documented in the patient record.
5. Documentation to be provided by the local physician will include drug administration records, progress notes, reports of protocol required laboratory and diagnostic studies and documentation of any hospitalizations.
6. The home physician will be requested to report to the MDACC physician investigator all life threatening events within 24 hours of documented occurrence.
7. Patients will return to MDACC every 8 weeks for evaluation.

8. Patients on pazopanib/torisel who have reached 12 months without progression may see their local physician and will return to MDACC every 8-16 weeks for evaluation and restaging.

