- g. Female patients of child-bearing age must have a negative pregnancy test within 7 days of beginning treatment.
- h. Patients receiving pazopanib only
- i. Urinalysis. If patient has urine protein ≥ 300 on UA, a random UPC ratio should be ordered.
- j. CT Chest, abdomen and pelvis. MRI of the brain (bone scan, plain films) should be obtained as appropriate. MRI of the abdomen and/or CT scan of the brain can be substituted at the physician's discretion.
- k. Within 4 weeks of study entry
- l. Optional blood collection for future correlative studies will be drawn at baseline, every 8 weeks, and at Off Treatment Visit.
- m. Within 12 weeks of study entry
- n. Patients receiving pazopanib will have a follow-up ECG at C2D1, 12 weeks later, and every 16 weeks thereafter.
- o. Tissue will also be collected during procedures performed, at any time point, while patients are enrolled in this study. No new procedures will be required. This tissue will also be banked for future research related to immunologic response.
- p. Patients receiving temsirolimus
- q. In 30 days after stopping therapy
- r. Long-Term Follow-Up for survival will occur every 3 months from final study therapy. Follow-up will consist of a phone call, e-mail correspondence or medical record review.
- s. Every 2 weeks for the first 8 weeks (both arms). Temsirolimus patients every 4 weeks thereafter. Pazopanib patients every 8 weeks x 2 and every 16 weeks thereafter.
- t. Patients who are progression free after 1 year can have their imaging studies obtained every 16 weeks.

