Where HR is the hazard ratio (experimental:control). For sample size calculation purposes we assume that the median PFS in the temsirolimus arm is 60% that of the pazopanib arm (3.8 months versus 6.1 months). The sample size estimate is based on a one-sided log-rank test with type one error equal to 0.10 and power of 0.80.

We will conduct an interim analysis for futility after 42 events have been observed. If the p-value used to assess futility at the interim analysis is greater than 0.4798 we will stop the trial early for futility.

Secondary Objectives

Overall survival: Overall survival is calculated from day of therapy initiation to the date of death. Patients who are lost to follow-up will be censored at date of last contact.

We will use the Kaplan-Meier estimator to estimate the OS for each group of patients (control, experimental), and the log-rank statistic will be used to test for treatment differences. We will also use the Cox proportional hazards regression model to estimate the hazard ratio (experimental:control) for OS with a 95% confidence interval.

We will also assess the response rate and report 95% confidence intervals.

Additional analyses:

Demographics

For each treatment group (control, experimental), summary statistics will be provided for age, weight, baseline disease status and prior treatments.

Toxicities

Toxicities and side effects that will be evaluated include, but are not limited to infections, renal toxicity, hepatic toxicity, and pulmonary toxicity. Methods of assessment will include monitoring blood counts, and performing laboratory tests as indicated by clinical signs and symptoms. Evidence of toxicities or adverse events will be recorded at all clinic visits. All observed toxicities and side effects will be graded (NCI CTC-AE v. 4.0) for all patients and the degree of association of each with pazopanib or temsirolimus assessed. The incidence and severity of toxicities will be compared between the two treatment arms with Fisher's exact test.

Stratification Factors

The Pocock-Simon Minimization Method will be used to randomize patients according to the following stratification factors:

- Prior nephrectomy status (yes or no)
- Prior cytokine/vaccine therapy (yes or no)

The randomization program based on this method will be developed in the Department of Biostatistics and Applied Mathematics, and the program will be available via an intranet web site of MD Anderson Cancer Center.

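### As written, Section 5.4 schedules 8-weekly on-treatment urinalysis without naming an arm, while the study calendar limits it to pazopanib, and nothing says which governs for patients on temsirolimus.

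*Combined protocol and SAP*

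**What the plan says.** Section 5.4 (evaluation during initial or crossover treatment) deals with urine in one bullet of two sentences. It opens "Urinalysis (U/A) every 8 weeks. Patients who have urine protein", and the first of the two sentences names no arm. The second says that patients with urine protein of 300 or more "should have a random UPC ratio checked for pazopanib patients only".

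In the study calendar (Section 9.0), the urinalysis row has a cell in the 8-weekly column with footnotes h and i. Footnote h reads "Patients receiving pazopanib only". Footnote i says that at the same protein threshold "a random UPC ratio should be ordered", and names no arm. The screening cell of that row carries only the 14-day timing footnote.

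At baseline the arms are treated alike. Section 5.3.1 states "Patients will have a U/A", and the eligibility criteria in Section 4.1 set a urine-protein limit for everyone by "random urine protein:creatinine ratio (UPC") or a 24-hour collection.

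Section 13.0 lists renal toxicity among the toxicities to be evaluated, then states: "The incidence and severity of toxicities will be compared between the two treatment arms with Fisher's exact test".

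**The concern.** Two parts of the current text give different on-treatment schedules for the same test in patients on temsirolimus. Section 5.6 tells crossover patients to follow both the calendar and Section 5.4, so each is live and neither ranks above the other. Patients who cross over from pazopanib to temsirolimus meet the same uncertainty.

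Conduct could diverge in practice. Temsirolimus patients may have infusions with a local physician, who under Section 5.4 is sent the protocol abstract and the evaluation-during-treatment material. The calendar is not listed among those papers.

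The statistical stake is ascertainment. The recording table in Section 11.0 has phase II trials capture even grade 1 events judged at least possibly related, so low-grade urine findings can enter the data. Section 3.1.3 names proteinuria as a less common event of note with pazopanib, so a between-arm comparison of it is foreseeable. If one arm is tested every 8 weeks and the other has no scheduled test, a difference in recorded proteinuria partly reflects who was tested.

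**Working it through.** The plan states no figure to reproduce. The check sets the texts side by side and then counts scheduled tests.

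**Step 1: what each text schedules on treatment.**

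| Item | Section 5.4, plain reading | Section 5.4, if the qualifier covers the whole bullet | Calendar, footnotes h and i |
|---|---|---|---|
| Urinalysis, pazopanib | every 8 weeks | every 8 weeks | every 8 weeks |
| Urinalysis, temsirolimus | every 8 weeks | none | none |
| Follow-up UPC, pazopanib | if protein is 300 or more | if protein is 300 or more | if protein is 300 or more |
| Follow-up UPC, temsirolimus | none | none | no scheduled test to trigger it |

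The texts disagree on one row, and only on the plain reading of Section 5.4.

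**Step 2: which reading the wording favours.** The arm limit ends the second sentence, whose subject is the UPC ratio. Elsewhere in Section 5.4, arm-specific tests have the arm named beside them: weekly blood pressure, chemistry, blood counts, thyroid tests and ECG. By that pattern, a urinalysis sentence with no arm named applies to both. Against this, the second sentence is awkwardly built, and its ending could be an arm limit added for the whole bullet. The text favours the plain reading but does not settle it.

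**Step 3: size of the difference.** If tests fall at weeks 8, 16, 24 and so on, a patient on temsirolimus for t weeks has floor(t/8) scheduled tests under the plain reading and 0 under the calendar.

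- Section 3.2.3 gives a median temsirolimus treatment duration of 17 weeks in the cited phase 3 trial: floor(17/8) = 2, so 2 v 0.
- Section 13.0 assumes a median PFS of 3.8 months on temsirolimus: 3.8 × 52/12 = 16.5 weeks, and floor(16.5/8) = 2, so again 2 v 0.
- Still on drug at week 24: floor(24/8) = 3, so 3 v 0.
- Off drug before week 8: 0 v 0.

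**Step 4: what both texts secure in the temsirolimus arm.** Both require baseline urinalysis. Both order chemistry, including creatinine and BUN, every 2 weeks for 8 weeks and every 4 weeks thereafter. After week 8 this is more frequent than for pazopanib, which moves to every 8 weeks twice and then every 16 weeks. Kidney function is therefore followed in both arms under either schedule. Only events found by testing urine depend on which text is followed.

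**The case against.** The strongest reply is that there is no contradiction: the bullet ends with a pazopanib limit, and if that limit governs the whole bullet, Section 5.4 and the calendar agree. This is a possible reading, and it is why the point should not be called a flat contradiction. It does not dispose of the matter. It is not what the sentence says, and it would confirm that urine is routinely tested in one arm only, which Section 13.0 does not address.

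A second reply is that monitoring by drug is deliberate. Thyroid tests are for pazopanib, on-treatment lipids are for temsirolimus, and the temsirolimus safety section (3.2.5) does not mention proteinuria. Section 6.0 has no proteinuria-specific dose rule for either drug, and even on the plain reading a temsirolimus patient at the threshold gets no on-treatment UPC. All of that stands. It keeps the point small, but does not tell a site which schedule to follow.

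A reader might infer more than the documents support:

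- *Temsirolimus patients are never tested.* Not so. All have a baseline urinalysis and must meet the urine-protein criterion. Those who cross over join the pazopanib schedule, and Section 13.0 provides for laboratory tests prompted by signs and symptoms. The accurate statement is that the calendar schedules no urinalysis while a patient is on temsirolimus.
- *Acute renal failure, which Section 3.2.5 reports for temsirolimus, could be missed.* This does not follow, because creatinine and BUN are monitored in both arms.
- *All 45 planned control patients lose three tests.* Three applies only to a patient still on drug at week 24. A patient who stops before week 8 has none under either schedule.

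**Conclusion.** The point holds as a narrow drafting conflict with a small consequence for safety analysis. Read as written, Section 5.4 and the calendar differ on whether patients on temsirolimus have scheduled on-treatment urinalysis, and the documents do not say which governs. The size is about 2 v 0 tests for a patient treated for the median duration. That assumes tests fall at multiples of 8 weeks and that treatment lasts about as long as in the cited phase 3 trial. It also assumes that the arm limit in Section 5.4 belongs to the UPC ratio. If it belongs to the whole bullet, the schedules agree and what remains is unequal detection of urine findings.

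The effect is confined to urine-detected events such as proteinuria. PFS, the sample size and the error rates are unaffected. The documents do not establish which schedule was intended, and no choice is made here.

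**What to change.** Reconcile the urine bullet in Section 5.4 with the calendar's urinalysis row and footnotes h and i. State separately which arm or arms the 8-weekly urinalysis applies to, and which the follow-up UPC applies to. Section 5.6 relies on both places, so one consistent statement also settles crossover treatment.

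If either test remains in one arm only, add a sentence to Section 13.0 saying that urine-detected events are summarised for that arm and are not compared between arms with Fisher's exact test.

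The cost is a wording change in Section 5.4 or the calendar, plus at most one sentence in Section 13.0. The design, the primary analysis and the sample size do not change.
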